## **7.5. Adjustments for Multiple Comparisons**

Not applicable since no statistical test will be performed on the primary or secondary endpoint.

## **7.6. Demographic and Other Baseline Characteristics**

Continuous variables will be summarized with number of subjects (n), mean, standard deviation, median, and ranges. The frequency distributions (counts and percentages) will be given for categorical data.

This document is electronically controlled. Printed copies are considered uncontrolled.

**Confidential**

### **7.6.1. Baseline Demographics**

The following subject demographic data will be summarized.

- Age
- Gender
- Ethnicity
- Race
- Height
- Weight

### **7.6.2. Smoking History**

The following smoking history data will be summarized:

- History of tobacco use (Yes/No, if yes, current/former)
- Tobacco use: type of tobacco, duration of use, # of units, and use frequencies

### **7.6.3. Cancer Diagnosis**

The following cancer diagnosis data will be summarized:

- Primary cancer type
- Tumor pathology
- Months since primary cancer diagnosis
- Target tumor type
- Location of target tumor
- Prior cancer treatments
  - Cancer type
  - Years of since previous cancer diagnosis
  - Cancer treatment
  - Months since last cancer treatment

### **7.6.4. Medical History**

The following medical history data will be summarized:

- Has the patient ever had surgery in the thoracic space? (unrelated to Lung Cancer treatment)
- Previous lung disease diagnosis

This document is electronically controlled. Printed copies are considered uncontrolled.

**Confidential**

## 7.7. Treatment Characteristics

Continuous variables will be summarized with number of subjects (n), mean, standard deviation, median, and ranges. The frequency distributions (counts and percentages) will be given for categorical data

### 7.7.1. Planning Application

Planning application characteristics:

- Axial two-dimensional measurement - maximum axial length
- Axial two-dimensional measurement - perpendicular axial length associated within maximum axial length
- Planned antenna point of entry (intercostal space)
- Planned approach
- Planned ablation time
- Planned ablation power
- Planned tip distance
- Planned insertion depth
- Target tumor width (X)
- Target tumor height (Y)
- Target tumor depth (Z)
- Calculated target tumor volume from planning application
- Predicted ablation zone width (X)
- Predicted ablation zone height (Y)
- Predicted ablation zone depth (Z)
- Predicted ablation zone volume
- Predicted minimum margin
- Predicted maximum margin

This document is electronically controlled. Printed copies are considered uncontrolled.

**Confidential**

### **7.7.2. Ablation Procedure**

Procedural characteristics:

- Duration of anesthesia (min)
- Type of anesthesia
- Duration of antenna placement (min)
- Antenna length
- Number of passes through the gantry for placement
- Actual approach
- Duration of ablation time (min)
- Actual ablation power

### **7.7.3. CT Imaging**

CT imaging characteristics:

- Pre-procedure image quality
- Lesion location
- Longest axial diameter
- Perpendicular diameter
- Tumor volume
- Critical structures within 10mm of tumor border
- Distance from tumor
- Intra-procedural image quality
- Radiating section of antenna of tumor center
- Tip to tumor margin
- Post-procedural image quality
- Ablation zone Width x
- Ablation zone Width y
- Ablation zone Depth z
- Tip distance
- Calculated ablation zone volume
- Needle depth
- Ablation zone shape

This document is electronically controlled. Printed copies are considered uncontrolled.

**Confidential**

- Presence of cavitation
- Maximum margin
- Minimum margin
- Location of areas with margins less than 0.5mm

## 7.8. Interim Analyses

Interim analyses will be conducted once the first 15 tumors are ablated. The interim analyses will be performed by following the same principle defined in this statistical analysis plan.

## 7.9. Evaluation of Objectives

### 7.9.1. Primary Endpoint

The primary endpoint is dose response immediately post-procedure and prior to surgical resection and is defined as the percentage change from the predicted outcome to the actual outcome.

The predicted values are from the PLAN CRF:

- Predicted ablation zone width (X)
- Predicted ablation zone height (Y)
- Predicted ablation zone depth (Z)
- Predicted ablation zone volume
- Calculated ablation zone volume (calculated from predicted X, Y, and Z value)

$$\text{Calculated Ablation Zone Volume} = \frac{4 * 3.14}{3} * \frac{\text{Predicted Ablation Zone Width} * \text{Height} * \text{Depth}}{8}$$

- The predicted ablation zone shape is the calculated ratio of predicted ablation zone width (X) and ablation zone height (Y)

$$\text{Predicted Ablation Zone Shape} = \frac{\text{Predicted Ablation Zone Width}}{\text{Predicted Ablation Zone Height}}$$

The actual values are from the IMAGE CRF:

- Width (X)
- Height (Y)
- Depth (Z)
- Ablation zone volume

$$\text{Calculated Ablation Zone Volume} = \frac{4 * 3.14}{3} * \frac{\text{Actual Ablation Zone Width} * \text{Height} * \text{Depth}}{8}$$

- Ablation zone shape

$$\text{Ablation Zone Shape} = \frac{\text{Ablation Zone width}}{\text{Ablation Zone height}}$$

This document is electronically controlled. Printed copies are considered uncontrolled.

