5.3 Primary Effectiveness Endpoint: Dose Response

[figure not shown]
The primary endpoint of this study is dose response. Dose response will be assessed by comparing actual ablation zone size and volume to predicted ablation zone size and volume prescribed by the physician using the Emprint™ Procedure Planning Application, version 1.1. Dose response will be measured for each ablation zone using CT imaging immediately post ablation and prior to the surgical resection.

All measurements used to determine dose response will be measured and reported by an independent core imaging lab. To assess dose response, the following measurements will be taken:

Predicted Ablation Zone:

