Once antenna placement has been verified, the Emprint™ generator will be set by clinician to deliver the prescribed dose based on target tumor size plus a 0.5 cm margin and physician experience. Once the generator settings have been verified, the ablation will be initiated either by the investigator, using a foot switch, or radiology technician / scrub nurse, using the user interface on the generator.

Once the ablation is complete, the antenna will remain in place and the third CT image will be taken to evaluate the characteristics of the resulting ablation zone. The antenna will then be removed and the final CT image will be taken and will be used to identify adverse events that may have occurred during the ablation procedure.

Once the final CT image has been acquired, the ablation zone will be resected as scheduled, by the thoracic surgeon per standard surgical practice. The resected tissue will then be sent to the on-site pathology laboratory for sample preparation. The prepared samples will be sent to a core laboratory for histologic analyses.

If complications arise due to the microwave ablation, termination of the session will be determined at the discretion of the investigator according to the severity of the event and the extent of the intervention required.

CT imaging using a multidetector row helical CT scanner (minimum 8 detector) will be employed four times during the patients' enrollment in the study. The first three scans will be higher resolution to accurately measure target tumor size, antenna placement, and the ablation zone. The final CT will be a low dose scan to assess the presence of bleeding or pneumothorax that occurred during the ablation. Scan parameters for the first three scans will be as follows:

- Detector collimation – 1.5 mm or less
- Pitch < 1
- 120kVp
- Reference 100-140 mA (dependent upon body habitus). Auto mA may be left on, but all other dose reduction should be turned off.
- Scans will be performed with a breath hold at end inspiration with arms elevated over head if possible.
- No IV contrast.
- Images for 3D processing will be reconstructed at 1.5 mm with a 20% overlap using a standard kernel.

Scan parameters for the fourth low dose scan will be as follows:

- Detector collimation – 2.5 mm or less
- 120kVp

- Reference 40-80 mA (dependent upon body habitus)
- Scans will be performed with a breath hold at end inspiration with arms elevated over head if possible.
- No IV contrast.

1. Pre-procedure Scan

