An appropriate length Emprint™ percutaneous antenna (15 cm or 20 cm) will be placed into the target tumor under CT image guidance. An ablation zone will then be generated using a single application of a prescribed dose based on target tumor size. Following completion of the prescribed dose, a post ablation CT image will be taken. The antenna will then be removed and the planned surgical resection will be conducted as scheduled.

In addition, the following ablation-specific variables will be collected at the time of procedure:

- Date
- Ablation zone diameter of longest axis as determined through post-procedure CT imaging
- Ablation zone volume as determined through post-procedure CT imaging
- Ablation start and stop times
- Total ablation time
- Overall ablation procedure time from beginning of antenna placement to completion of the ablation.
- Antenna size
- Dose used
- Adverse events
- Device Deficiencies
- Procedural failures (e.g., failure of microwave application, patient factors that prematurely stop procedure, etc.)

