**Confidential**

The percentage change (calculated as  $100 \times (A-P)/P$ ) (where P=predicted and A=actual) will be calculated for each of the following measurements:

- Ablation zone width (X)
- Ablation zone height (Y)
- Ablation zone depth (Z)
- Ablation zone volume
  - ✓ Predicated ablation zone volume vs actual ablation zone volume
  - ✓ Calculated ablation zone volume (calculated from predicated X, Y, and Z value) vs. actual ablation zone volume
- Ablation zone shape

For each of the above measurements, the percentage change will be summarized with number of subjects (n), mean, standard deviation, median, and ranges. Summary will be done for all target tumors combined and for each target tumor type (primary, recurrent, and metastatic).

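### Must planned and delivered dose be paired tumor by tumor before the primary percentage change can be interpreted?

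*SAP*

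**What the plan says.** The protocol's section on the primary effectiveness endpoint sets the target: "Dose response will be assessed by comparing actual ablation zone size and volume to predicted ablation zone size and volume prescribed by the physician". SAP 7.9.1 carries this out as 100 × (A − P)/P. For P, "The predicted values are from the PLAN CRF"; A comes from the IMAGE CRF, that is, from the CT after ablation. Then "the percentage change will be summarized with number of subjects (n), mean, standard deviation, median, and ranges", for all target tumors and by tumor type.

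Dose appears elsewhere. SAP 7.7.1 lists planned time and "Planned ablation power". SAP 7.7.2 lists ablation duration and "Actual ablation power". Each is summarised on its own. Protocol 6.6.1 adds a by-subject listing of time and power under safety. No section sets planned and delivered values side by side for a tumor, or asks for a summary limited to tumors treated as planned.

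**The concern.** P belongs to the plan and A belongs to whatever was delivered. If the two doses differ, the percentage change no longer isolates how well the planning application predicts. A short ablation would look like over-prediction.

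The documents foresee some departures. Protocol 5.7.5 says that if complications arise, "termination of the session will be determined at the discretion of the investigator". It also records procedural failures, and protocol 8.7 names generator malfunction that ends a cycle early.

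Separate summaries of planned and actual dose would not reveal the mixing, because departures in opposite directions cancel in the group means. With at most 30 subjects, no sample-size basis and no test, the descriptive table is the evidence for technical performance, and a few tumors can set its minimum and widen its SD.

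**Working it through.** **1. The algebra.** Let Pd be the zone the application would predict at the delivered dose. Then A/P = (A/Pd) × (Pd/P). With illustrative values P = 20, Pd = 15 and A = 12, the ratio is 0.80 × 0.75 = 0.60. The reported change is −40%, made up of −20% prediction error and −25% dose departure. The mixing is real whenever Pd differs from P.

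**2. When the documents let Pd differ from P.**

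- *Choice of dose.* Protocol 5.2 and SAP 5 have ablation performed at the dose selected during planning. Protocol 5.7.5 says the prescription is established in the planning phase.
- *Generator setting.* It is "set by clinician to deliver the prescribed dose based on target tumor size plus a 0.5 cm margin and physician experience". Tumor size, margin and experience are the basis of the prescribed dose. The sentence does not describe a second choice made away from the plan.
- *Imaging.* "Following completion of the prescribed dose, a post ablation CT image will be taken". The normal path therefore has the full dose delivered before A is measured.
- *Early stop or device failure.* These are foreseen and recorded. SAP 7.1.3 defines MITT as subjects who *completed* ablation, which on its ordinary meaning leaves them out. Protocol 6.4 says *underwent*, which keeps them in.

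**3. Size, on assumptions.** The documents give neither the number nor the size of departures. Assume one tumor per subject, n = 30, two tumors at half energy, and volume proportional to energy to the power k, with k from 0.5 to 1.

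- Each affected tumor: 0.5^k − 1 = −29.3% (k = 0.5) to −50.0% (k = 1).
- Mean, other tumors exactly predicted: (2/30) × (−29.3 to −50.0) = −1.95 to −3.33 points.
- SD: √[2 × 28/(30 × 29)] × (29.3 to 50.0) = 0.2537 × (29.3 to 50.0) = 7.4 to 12.7, instead of 0.
- Median: 0, and it stays 0 until 15 of the 30 tumors are affected.

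Now let prediction error have mean 0 and an assumed SD of 20 points, and write g = 0.5^k. The mixture variance is (1 + 0.20²)(28/30 + 2g²/30) − (28/30 + 2g/30)².

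- g = 0.707: 1.04 × 0.9667 − 0.9805² = 0.0440, so the SD is 21.0.
- g = 0.5: 1.04 × 0.9500 − 0.9667² = 0.0536, so the SD is 23.1.
- Without departures the SD is 20.0. The standard error of the mean is 20/√30 = 3.65, which is larger than the shift of 1.95 to 3.33.

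More departures matter more. Three of 30 tumors with Pd/P = 0.5 move the mean by 3/30 × 50 = 5.0 points, and six move it by 10.0. At the 15-tumor interim, two tumors at half energy move it by 2/15 × (29.3 to 50.0) = 3.9 to 6.7 points. With no departures every figure is 0.

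**The case for a change.** The strongest case for a change is this. *Completed* is not defined in terms of planned power and time, so it would not screen out an ablation finished at a different power or run longer. The dose listing does not say whether it is planned or delivered. If each tumor had a 5% chance of departing from plan (an assumption), at least one of 30 would do so with probability 1 − 0.95^30 = 79%. Departures can also hide: one tumor at +50% and one at −50%, the rest exact, leave the mean at 0 with an SD of 13.1. A per-tumor table would cost little.

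Much of this stands as a remark about reporting. The pairing is not prespecified, and a careful analyst would look at it. It does not show that the plan as written misleads:

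- The documents describe no route to a completed ablation at a dose other than the planned one.
- The fields for the check are collected under SAP 7.7.1 and 7.7.2. SAP 7.1.3 lets further sub-populations be defined, and SAP section 3 allows documented departures from the plan.
- A summary restricted to on-plan tumors has its own costs: a smaller n, the possible loss of difficult cases, and a tolerance that may be chosen after the data are seen.

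The difference between *underwent* and *completed* is a genuine inconsistency, but it concerns who is analysed. Pairing the doses would not resolve it.

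**Conclusion.** No change follows on this point. The percentage change measures agreement between plan and result, which is what the protocol defines as its primary endpoint, and nothing in it is computed wrongly. The two readings of MITT affect what the summary includes, not whether it can be used. If early-stopped ablations are out, the foreseen dose departures go with them. If they are in, a shortfall in delivery is arguably part of the technical performance that SAP section 4 sets out to show.

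The missing pairing is a gap that analysts can fill from existing fields in a data set of at most 30 subjects. The documents do not show that any tumor was treated off plan. Under the two-of-30 assumption the mean moves by 2.0 to 3.3 points, the SD rises from 20.0 to between 21.0 and 23.1 against an assumed 20-point scatter, and the range changes only if an affected tumor is extreme. Larger effects need more departures than the documents give reason to expect. SAP 7.5 confirms that no test is performed, and no acceptance threshold is stated, so no decision turns on the result.

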**Confidential**

The percentage change (calculated as  $100 \times (A-P)/P$ ) (where P=predicted and A=actual) will be calculated for each of the following measurements:

- Ablation zone width (X)
- Ablation zone height (Y)
- Ablation zone depth (Z)
- Ablation zone volume
  - ✓ Predicated ablation zone volume vs actual ablation zone volume
  - ✓ Calculated ablation zone volume (calculated from predicated X, Y, and Z value) vs. actual ablation zone volume
- Ablation zone shape

For each of the above measurements, the percentage change will be summarized with number of subjects (n), mean, standard deviation, median, and ranges. Summary will be done for all target tumors combined and for each target tumor type (primary, recurrent, and metastatic).

### **7.8.2. Secondary Endpoint**

Complete tumor ablation immediately post-procedure will be measured for each target tumor using histologic analysis to evaluate complete ablation at the cellular level.

All histology samples will be evaluated by a core laboratory. Both vital staining (Nicotinamide adenine dinucleotide (NADH) assay) and structural staining (hematoxylin and eosin; H&E) techniques will be used to evaluate cellular integrity within the ablation zone.

The histology data for the NADH assay is from the NADH Sample Analysis – Part 1 of the PATHOLOGY CRF:

- If the “Evidence of Complete Ablation” is checked Yes, it is complete tumor ablation
- If the “Evidence of Complete Ablation” is checked No and the “If No, Was Delayed Necrosis Achieved” is checked Yes, it is delayed necrosis
- If the “Evidence of Complete Ablation” is checked No and the “If No, Was Delayed Necrosis Achieved” is checked No, it is incomplete tumor ablation

The histology data for the H&E assay is from the H&E Sample Analysis – Part 2 of the PATHOLOGY CRF:

- If the “Evidence of Complete Ablation” is checked Yes, it is complete tumor ablation
- If the “Evidence of Complete Ablation” is checked No, it is incomplete tumor ablation

The number and percentage of tumors which achieve complete tumor ablation, delayed necrosis and incomplete tumor ablation for all target tumors combined and for each target tumor type (primary, recurrent, and metastatic) will be provided. The summary will be provided by NADH assay, H&E assay, and NADH and H&E combined.

This document is electronically controlled. Printed copies are considered uncontrolled.

**Confidential**

### **7.10. Safety Evaluation**

Adverse events for all enrolled subjects will be collected and reported. All reported adverse events will be presented based on the ITT population and tabulated by system organ class and preferred term. The incidence of peri-procedural and post-procedural events related to the actual procedure or the study device will be summarized and reported using counts, and percentages.

### **7.11. Health Outcomes Analyses**

NA.

### **7.12. Changes to Planned Analysis**

NA.

---

## **8. Validation Requirements**

Primary and secondary endpoints will be validated by level I validation and the rest of the tables, listings and figures will be validated by level II validation.

Level I: The peer reviewer independently programs output and then compares the output with that generated by the original Statistical Programmer. Define the level of validation required for each objective or analysis output.

Level II: The peer reviewer reviews the code; where appropriate, performs manual calculations or simple programming checks to verify the output.

This document is electronically controlled. Printed copies are considered uncontrolled.

**Confidential**
